### 10.1 Definitions/Classifications

Definitions according to ISO 14155:2011 will be used in this study.

Where the definition indicates “device”, it refers to any product used in the study. See product description section 6 for product information.

**Table 3. Definition of Adverse Events and Device Deficiency**

Term	Abbreviation	ISO Definition
Adverse Event	AE	
Any untoward medical occurrence, unintended disease or injury, or untoward clinical signs (including abnormal laboratory findings) in subjects, users or other persons, whether or not related to the investigational medical device.
 
NOTE 1: This definition includes events related to the investigational medical device or the comparator.
 
NOTE 2: This definition includes events related to the procedures involved.
 
NOTE 3: For users or other persons, this definition is restricted to events related to investigational medical devices.

Adverse Device Effect	ADE	
Adverse event related to the use of an investigational medical device.
 
NOTE 1: This definition includes adverse events resulting from insufficient or inadequate instructions for use, deployment, implantation, installation, or operation, or any malfunction of the investigational medical device.
 
NOTE 2: This definition includes any event resulting from use error or from intentional misuse of the investigational medical device.

Serious Adverse Device Effect	SADE	Adverse device effect that has resulted in any of the consequences characteristic of a Serious Adverse Event.

Term	Abbreviation	ISO Definition
Serious Adverse Event	SAE	
An adverse event that
 

1. led to death,

2. led to serious deterioration in the health of the subject, that either resulted in

3. resulted in a life-threatening illness or injury, or

4. resulted in a permanent impairment of a body structure or a body function, or

5. resulted in-patient or prolonged hospitalization, or

6. led to a medical or surgical intervention to prevent life-threatening illness or injury or permanent impairment to a body structure or a body function,

7. led to fetal distress, fetal death or a congenital abnormality or birth defect.

 
NOTE: Planned hospitalization for a pre-existing condition, or a procedure required by the CIP, without serious deterioration in health, is not considered a serious adverse event.

Unanticipated Serious Adverse Device Effect	USADE	
Serious adverse device effect which by its nature, incidence, severity or outcome has not been identified in the current version of the risk analysis report.
 
NOTE: Anticipated serious adverse device effect (ASADE) is an effect which by its nature, incidence, severity or outcome has been identified in the risk analysis report.

Device Deficiency	DD	
Inadequacy of a medical device with respect to its identity, quality, durability, reliability, safety or performance.
 
NOTE: Device deficiencies include malfunctions, use errors, and inadequate labelling.

## 10.2 Reporting of Adverse Events

AE information will be collected throughout the study and reported to Medtronic on an AE eCRF, one for each adverse event. It is the responsibility of the investigator to identify the occurrence of adverse events to ensure that the information is accurately documented in the medical record and on the eCRFs.

Device Deficiency (DD) information will also be collected throughout the study and reported to Medtronic on a Device Deficiency eCRF. DDs require immediate reporting if they did not lead to an adverse event but could have led to a serious adverse device effect (SADE):

- if either suitable action had not been taken,
- if intervention had not been made, or
- if circumstances had been less fortunate

AE documentation will include the following information at a minimum:

- Date of event

- Time of the event
- Diagnosis and description (including confirmation of respiratory nature)
- Actions taken / treatment (including vital signs, and date and time of rescue related actions when applicable)
- Assessment of seriousness
- Relatedness to the event (including opioid therapy or device)
- Outcome or resolution and date of the resolution

For AEs that require immediate reporting, initial reporting may be done by phone, fax, e-mail, or preferably on the eCRF completing as much information as is available. The completed AE eCRF must be sent to Medtronic as soon as possible.

In case the investigator requires information from the sponsor in an emergency situation, the investigator can contact Technical Services or the Medtronic Study Manager. Contact information will be provided under separate cover.

The sponsor will ensure timely Adverse Event reporting to meet local regulatory requirements.

A list of anticipated adverse events that are expected in nature is included in Appendix A of this CIP.

**Table 4. Reporting Requirements for Events**

Serious Adverse Device Effects (SADE), including Unanticipated Serious Adverse Device Effect (USADE):	
Investigator submit to:	
Medtronic	Immediately after the investigator first learns of the event or of new information in relation with an already reported event.
Regulatory Authority	As per local reporting requirement.
EC	Submit to EC per local reporting requirement.
Sponsor submit to:	
Regulatory Authorities	Reporting timeframe as per local requirement.
EC	Submit to EC per local reporting requirement.
Serious Adverse Events (SAE)	
Investigator submit to:	
Medtronic	Immediately after the investigator first learns of the event or of new information in relation with an already reported event.

Regulatory Authority	As per local reporting requirement.
EC	Submit to EC per local reporting requirement.
Sponsor submit to:	
Regulatory Authorities	Reporting timeframe as per local requirement.
EC	Submit to EC per local reporting requirement.
Adverse Device Effects (ADE)	
Investigator submit to:	
Medtronic	Immediately after the investigator first learns of the event.
Regulatory Authority	As per local reporting requirement.
EC	Submit to EC per local reporting requirement.
Sponsor submit to:	
Regulatory Authorities	Reporting timeframe as per local requirement
EC	Submit to EC per local reporting requirement.
All other AEs	
Investigator submit to:	
Medtronic	Submit in a timely manner after the investigator first learns of the event.
Regulatory Authority	As per local reporting requirement.
EC	Submit to EC per local reporting requirement.
Device Deficiency with SADE potential	
Investigator submit to:	
Medtronic	Immediately after the investigator first learns of the deficiency or of new information in relation with an already reported deficiency.
Regulatory Authorities	As per local reporting requirement.
EC	As per local reporting requirement.
Sponsor submit to:	

Regulatory Authorities	As per local reporting requirement.
EC	As per local reporting requirement.
All other Device Deficiencies	
Investigator submit to	
Medtronic	Submit in a timely manner after the investigator first learns of the deficiency.
Regulatory Authorities	As per local reporting requirement.
EC	As per local reporting requirement.

## 10.3 Patient deaths

All patient deaths and adverse events that lead to death must be reported by the investigator to Medtronic. Initial reporting may be done by phone, fax, e-mail, or preferably on the eCRF completing as much information as is available. The completed AE eCRF must be sent to Medtronic as soon as possible after the investigator first learns of the death.

## 10.4 Complaint reporting

A Product Complaint is any written, electronic or oral communication that alleges deficiencies related to the identity, quality, durability, reliability, safety, effectiveness or performance of a medical device that has been placed on the market.

Market-released devices require product complaint reporting. The reporting of product complaints is not part of the clinical study and should be done via regular channels for product complaint reporting in addition to the AE reporting requirements. Refer to local regulations for reporting requirements.

## 11. Clinical Event Committee

This study will not have a Clinical Event Committee (CEC).

Since only two German sites will be involved, assessment of study specific endpoints and/or events will be performed by delegated site sub-Investigators that will perform cross-site events assessment

## 12. Statistical Design and Methods

### 12.1 Sample size justification

The sample size calculation is based on primary endpoint and it was estimated using data from previous studies with a precision-based calculation. Recent data on post-surgical patient have shown a proportion of patient with the RC markers for the SpO2 ≤ 85% for ≥ 3 minutes at 13% and for RR ≤ 8 or ≥ 22 bpm

for  $\geq 3$  minutes at 1.4% in patients undergoing opioid therapy. Using this information, a minimum proportion of 10% of patients with RC markers with a sample size of 260 patients will be able to obtain a 95% confidence level with a precision of 5% (ranging from 5% to 10%) and a power of at least 0.80 defined as the probability of achieving the desired precision. Considering a 10% withdrawal or potential dropouts and a potential attrition rate to monitoring compliance of 5% a total of approximately 210 patients will be enrolled. This cohort will be used prospectively for the blinded and not blinded phase with a ratio 1:2 respectively to minimize not blinded monitored patients. The blinded phase will enroll 70 patients randomly allocated 1:1 in the Capnostream 20p and PM1000N-RR arm while the not blinded phase will enroll 140 patients with same randomized schedule.

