The analysis of primary objective will be based on the proportion of patients with at least one RC marker; it will be reported together with their 95% confidence intervals and separately for each arm and phase of the study. When comparison of clinical primary outcomes is conducted the propensity score methods could be used to control for biases and confounding which may occur due to the nature of this study. For all secondary outcomes the logistic regression model will be used to check potential predictors.

Bivariate odds ratios (ORs) and 95% confidence intervals (95% CIs) will be estimated for each predictor. A multivariate logistic regression model will be performed according to univariate model's results. Other secondary outcomes will be performed using sensitivity and specificity analysis.

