## 12.3 Analysis of clinical data

Patient demographics and baseline characteristics will be presented using appropriate summary statistics. This includes mean and standard deviation, minimum, maximum and median with the interquartile range [IQR] for continuous variables and counts and percentages for categorical variables. Summary statistics will be reported with maximum 2 decimals, as appropriate. The SAS software (SAS Institute Inc., Cary, NC, USA) will be used to perform statistical analyses. Statistical tests will be based on a two-sided significance level of 0.05. Graphical representations will be used as deemed appropriate. No adjustments for multiple comparisons or multiple look at data will be performed. Outliers and influential observations will be identified via graphical plots and according to study team decision the analysis could be repeated excluding potential outliers. In case of missing data, no imputation method will be implemented for analysis.

The Full Analysis Set (FAS) will be used for primary final analysis. Any patient who does not satisfying the inclusion/exclusion criteria will be eliminate from the FAS population. Details of endpoints analyses and additional analysis will be described in the Statistical Analysis Plan. The analyses of primary objective on the proportion of patient with at least one RC markers will be reported together with their 95% confidence intervals and separately for each arm and phase of the study (see primary endpoint definition). When comparison of clinical primary outcomes is conducted the propensity score methods could be used to control for biases and confounding which may be due to the nature of this study. The

difference between the two groups within phase and between phases within groups will be analyzed by means of unpaired t-test or Mann-Whitney test according to the normal or non-normal distribution. For one secondary outcome the logistic regression model will be used to check potential predictors. Bivariate odds ratios (ORs) and 95% confidence intervals (95% CIs) will be estimated for each predictor. A multivariate logistic regression model will be performed according to univariate model's results. Other secondary outcomes will be performed using sensitivity and specificity analysis.

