## 6. Determination of Sample Size

The sample size calculation is based on primary endpoint and it was estimated using data from previous studies with a precision-based calculation. Recent data on post-surgical patient have shown a proportion of patient with the RC markers for the  $\text{SpO}_2 \leq 85\%$  for  $\geq 3$  minutes at 13% and for  $\text{RR} \leq 8$  or  $\geq 22$  bpm for  $\geq 3$  minutes at 1.4% in patients undergoing opioid therapy. Using this information, a minimum proportion of 10% of patients with RC markers with a sample size of 182 subjects will be able to obtain a 95% confidence level with a precision of 5% (ranging from 5% to 10%) and a power of at least 0.80 defined as the probability of achieving the desired precision. Considering a 10% withdrawal or potential dropouts and a potential attrition rate to monitoring compliance of 5% a total of approximately 210 subjects will be enrolled. This cohort will be used prospectively for the blinded and not blinded phase with a ratio 1:2 respectively to minimize not blinded monitored subjects. The blinded phase will enroll

70 subjects randomly allocated 1:1 in the Capnostream 20p and PM1000N arms while the not blinded phase will enroll 140 subjects with same randomized schedule.

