**Table 3 - Protocol Deviation by Reason - FAS**

**Table 4 - Protocol Deviation by Visit - FAS**

**Listing 1 - Other deviations – FAS**

### 7.1.3. Analysis Sets

The following patient sets will be used for the analysis:

- The Full Analysis Set (FAS) includes all patients actively enrolled in the study, who signed Informed Consent Form (ICF), fulfilled the inclusion/exclusion criteria and monitored by CS20p or PM1000N. The FAS will be used to describe both baseline characteristics and safety outcomes of the study population;
- The Per Protocol Set (PPS) includes all patients in the FAS, without major protocol deviations, who have at least 24 hours of monitoring *effective time*. The PPS will be used to describe baseline characteristics of the study population and to evaluate the primary and secondary endpoints. Patient with poor quality of device data, defined as having less than 90% of time continuously monitored, will be included or excluded from the PPS, as appropriate.

The following table shows how each population set will be used for analyses:

Population set	Baseline assessment	Primary and Secondary Endpoint #1	Secondary Endpoints #2, #3, #4 and #5	Safety AE Death
FAS	✓		✓	✓
PPS	✓	✓	✓	

For those patients who have less than 24 hours or poor quality of device data monitoring or who withdrew, the analyses will include all data up to the point of their last data collection only for FAS population.

An additional set could be created during the analysis phase, in case necessary to investigate on a particular subgroup of patients.

 Effective time is the cumulative time with valid recorded data. This aimed to filter out periods of time where the patient was not connected to the Capnography cannula or pulse-ox sensor, but recording was on-going (the patient was not monitored during this time).

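### Protocol 12.1 states a required sample of 260 but enrols about 210 (SAP 6 has 182, which reproduces), and the ±5-point precision fits the whole cohort, not the primary proportions reported by arm and phase

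*Protocol*

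**What the plan says.** Protocol 12.1 justifies the sample size by precision alone. It takes "a minimum proportion of 10% of patients with RC markers with a sample size of 260 patients" as giving a 95% interval with 5% precision, with probability at least 0.80 of achieving it. A bracket after the 5% mentions a range of 5% to 10% and is not explained. The section then allows 10% for withdrawal and 5% for monitoring non-compliance and concludes that "a total of approximately 210 patients will be enrolled": 70 in Phase I and 140 in Phase II, each randomised 1:1.

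SAP 6 repeats the paragraph with one change. It says "with a sample size of 182 subjects will be able to obtain a 95% confidence level with a precision of 5"%, and reaches the same 210.

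The 10% is called a minimum. It is drawn from two published rates: SpO2 "≤ 85% for ≥ 3 minutes at 13"%, and abnormal respiratory rate at 1.4%. The primary endpoint (Protocol 4.1.1) uses SpO2 ≤ 90%, plus respiratory rate and, in the Capnostream arm only, etCO2 and apnea.

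On reporting, the Synopsis says of the primary proportion that "it will be reported together with their 95% confidence intervals and separately for each arm and phase of the study", and Protocol 12.3 repeats this. The analysis set differs between documents. Protocol 12.3: "The Full Analysis Set (FAS) will be used for primary final analysis". SAP 7.1.3: "The PPS will be used to describe baseline characteristics of the study population and to evaluate the primary and secondary endpoints". SAP 7.9.1 says that a proportion and a rate will be reported, without giving a unit for the proportion, and then specifies person-time rates by arm and phase.

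**The concern.** There are two difficulties. First, a number needed before losses cannot exceed the number enrolled after allowing for losses, and two current documents give different required numbers (260 and 182). A reader of the protocol alone would conclude that the trial enrols fewer patients than its own calculation demands.

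Second, precision is the only argument for the sample size, and incidence is the primary objective, so interval width is in effect the planned result. The calculation treats one cohort, while the primary proportion is to be reported in four cells of at most 35, 35, 70 and 70 patients. Anyone who carries the ±5 over to those cells will expect intervals much narrower than the trial can give. The planning rate also comes from a stricter desaturation threshold than the endpoint uses, so the true rate may be higher and every interval wider.

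**Working it through.** **Inputs.** From Protocol 12.1 and SAP 6: rate p = 0.10 (cited SpO2 rate 0.13); 95% interval; precision 5 points, read here as the half-width; probability of achieving it ≥ 0.80; losses 10% and 5%; 70 + 140 patients, 1:1. From Protocol 3.1: up to 37% of patients with saturation < 90% for more than one hour, from the same reference as the 13%.

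**Formulas.** Expected half-width = 1.96 × √(p(1 − p)/n). Probability of ±5 = sum of binomial probabilities over the counts whose 95% half-width is ≤ 0.05, with Wald and with exact (Clopper-Pearson) intervals.

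**Step 1: the plan's own figure.** At p = 0.10, the smallest n with probability ≥ 0.80 is about 165 (Wald) or 179 (exact). SAP 6's 182 fits the exact calculation: the probability there is 0.935 Wald and 0.855 exact. At n = 260 the probability is about 1.00, so 260 is not the solution under either method.

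**Step 2: losses.** 182 × 1.15 = 209.3, and 182/(0.90 × 0.95) = 212.9. Both fit about 210. In contrast, 260 × 1.15 = 299 and 260/(0.90 × 0.95) = 304. The version history records a change of the total from 300 to 210, so 260 is probably left over from the earlier total. That explanation is an inference; the contradiction in the current text is not.

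**Step 3: how far the ±5 reaches.** With 182 evaluable, the probability stays ≥ 0.80 for rates up to about 10.4% (exact) or 11.4% (Wald). With all 210 evaluable, it does so up to about 12.6% or 14.4%. At the cited 13%, n = 182 gives an expected half-width of 4.9 points but a probability of only 0.584 Wald / 0.409 exact; n = 210 gives 0.927 / 0.749.

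**Step 4: the reported cells.** Without losses the cells are 35 and 70 (an upper bound for the FAS). With planned losses they are 35 × 0.855 = 29.9 and 70 × 0.855 = 59.9, and Phase II overall is 140 × 0.855 = 119.7.

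| Estimate | n | Half-width at 10% | at 13% | at 37% | Probability of ±5 at 10% (Wald / exact) |
|---|---|---|---|---|---|
| Phase I arm, no losses | 35 | 9.9 | 11.1 | 16.0 | 0.025 / 0.000 |
| Phase I arm, planned losses | 30 | 10.7 | 12.0 | 17.3 | 0.042 / 0.000 |
| Phase II arm, no losses | 70 | 7.0 | 7.9 | 11.3 | 0.071 / 0.024 |
| Phase II arm, planned losses | 60 | 7.6 | 8.5 | 12.2 | 0.053 / 0.014 |
| Phase II, both arms, no losses | 140 | 5.0 | 5.6 | 8.0 | 0.571 / 0.348 |
| Phase II, both arms, planned losses | 120 | 5.4 | 6.0 | 8.6 | 0.336 / 0.141 |
| Whole cohort | 182 | 4.4 | 4.9 | 7.0 | 0.935 / 0.855 |

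Example: 1.96 × √(0.10 × 0.90/35) = 0.099. Phase I with both arms together (70, or 60 after losses) has the same widths as a Phase II arm. The Wald probabilities at n = 30 and 35 come only from the zero-event outcome, where the Wald interval has zero width (0.9^35 = 0.025).

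Relative to 5 points, the half-widths at 10% are 9.9/5 = 2.0 to 10.7/5 = 2.1 times in Phase I arms, and 7.0/5 = 1.4 to 7.6/5 = 1.5 times in Phase II arms.

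These widths are for proportions. They do not describe the person-time rates of SAP 7.9.1.

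**The case against.** The best defence has four parts.

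- *The 260 is editorial.* SAP version 1.1 was aligned with protocol version 2.0 and has 182, and every operational number (210, 70, 140) agrees across the documents. This stands. A reader might infer from the 260 that the trial is undersized; the documents do not support that, because 182 reproduces and 210 covers it. The figure is still wrong in the governing document.
- *The plan never promises ±5 for each arm and phase.* This also stands. A reader might infer such a promise because the primary proportion is reported that way, but Protocol 12.1 sizes one cohort and then divides it. The gap is that neither document says which estimate the ±5 covers or gives any width for the cells.
- *The bracketed 5% to 10% may be a range of half-widths.* That is possible: at 10% without losses, the widths run from 5.0 (n = 140) to 9.9 (n = 35). But the bracket is tied to no cell, 30 per arm gives 10.7, and 35 per arm reaches ±10 with probability only 0.31 (exact) to 0.53 (Wald). It could equally be a slip for an interval around 10%, which would run from 5% to 15%. Only the sponsor can say.
- *A pooled proportion may be intended.* SAP 7.9.1 mentions a proportion without stratifying it, and SAP 7.9.2 compares phases without separating arms. A reader might infer that the different marker sets (four against two) rule out a pooled result. No section says so, and that reason should not be written into the plan on the sponsor's behalf.

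**Conclusion.** The concern holds in two parts. The 260 in Protocol 12.1 is a wrong figure in current text; 182 is the figure that reproduces and leads to 210. No precision is lost by this.

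The stated ±5 points with probability ≥ 0.80 is met by the whole cohort at rates up to about 10%, and does not describe the arm-by-phase proportions. At the plan's own 10%, those have about twice the stated half-width in Phase I arms and 1.4 to 1.5 times in Phase II arms. The conclusion is the same for FAS or PPS, with or without losses, and for Wald or exact intervals. It assumes that precision means half-width.

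A rate well above 10% is plausible. The 13% is for SpO2 ≤ 85%, the endpoint uses ≤ 90% and further markers, and Protocol 3.1 cites up to 37% below 90% for over an hour. At 37%, the whole cohort gives about ±7.0, Phase I arms ±16.0 to ±17.3, and Phase II arms ±11.3 to ±12.2. The 37% is an illustration from the protocol's background and not a forecast: it is an upper figure, and cross-site adjudication under SAP 7.9.1 may lower the count.

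This should be fixed, but it does not call the enrolment target into question.

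**What to change.** Keep 210 patients.

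1. In Protocol 12.1, replace 260 with 182.
2. In Protocol 12.1 and SAP 6, state that ±5 points with probability ≥ 0.80 applies to the pooled cohort of about 182 evaluable patients at rates up to about 10%.
3. In the same places, state the expected 95% half-widths of the arm-by-phase proportions, without losses / with planned losses, at 10%, 13% and a higher rate consistent with Protocol 3.1, for example 37%. Phase I arms (n = 35/30): ±9.9/±10.7, ±11.1/±12.0, ±16.0/±17.3. Phase II arms (n = 70/60): ±7.0/±7.6, ±7.9/±8.5, ±11.3/±12.2. Label these as widths for proportions, not for the person-time rates of SAP 7.9.1.
4. Say that the 10% derives from an SpO2 ≤ 85% threshold, and correct or explain the bracketed 5% to 10%.
5. The sponsor should state whether a pooled proportion will be reported.

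Cost: one number and a few sentences in each document, with no extra patients, data or analyses. The downside is that the stated precision becomes less favourable, most visibly for the Phase I arms.
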